3.1.1 Screening Phase

Patients will be screened upon admission to the Vascular Neurology non-intensive care unit service. As part of standard intake procedures, a physician on the admitting team will determine patient study eligibility. There will be no extra evaluations or laboratory tests needed at the screening visit.

As this is a comparison of two effective nursing models, both of which are available and employed in clinical practice, the study is of minimal risk to patients. All patients will receive a standard treatment currently in use at our facility. Patients may be unaware of our ongoing comparative effectiveness trial while they are hospitalized. However, informed consent will be obtained at the time of follow up phone calls.

3.1.2 Study Intervention Phase

All of the standard medical care will be identical in both arms of the study. Health literacy will be assessed in all patients upon admission to assure educational interventions are directed accordingly. Patients who

are assigned to standard nursing care will receive standard care which includes educational interventions from staff nurses in keeping with current Joint commission and AHA/ASA guidelines. Patients assigned to routine care will not interact with the attending nurse. Patients who are assigned to the intervention will receive additional patient-centered supplementary care and education from the attending nurse.

3.1.2 Follow Up Phase

Patients will be followed for a total of 90 days following discharge from the hospital. Patients will be contacted at 7, 30, and 90 days following discharge via telephone call. When patients are unable to communicate their own views due to aphasia or other disability, caregivers will be asked to answer the applicable survey questions.

3.1.3 Allocation to Interventional Group

Stroke patients who are admitted on even-numbered weekdays and enrolled in this trial will be assigned to care with an attending nurse; patients admitted on odd-numbered weekdays will get usual routine care. The attending nurse will query the electronic medical record as well as communicate with the physician team so that all incoming admissions on even-numbered days to the Vascular Neurology service are known to the attending nurse.

3.2 Study Endpoints

3.2.1 Primary Study Endpoints

- Primary endpoints will be stroke education retention as measured by the SPER and medication adherence as measured by MMAS-4 as these are the areas where we anticipate the largest potential effect of the nurse attending. The mean scores on these two tests will be compared between groups at each time interval that they are administered.

3.2.2 Secondary Study Endpoints

- We will compare the results of the newly designed survey questionnaire to capture patient impression of their in-hospital care, transition home, and quality of life.
- The results of the SIS will be captured at 30 days and compared between groups.
- The proportion of patients with readmissions within 30 days will be compared between groups at 30 days.
- A global statistic that incorporates all survey measures to determine whether the attending nurse model of care is consistently and persuasively more effective than routine nursing care will be compared between groups.

3.2.3 Primary Safety Endpoints [if applicable]

As this is a comparative effectiveness study of two models of nursing care that are currently both in use so there are no safety endpoints. Safety data will be collected during patients in hospital stay in keeping with current quality control process.

4 Study Population and Duration of Participation

4.1 Inclusion Criteria

- > 18 years of age
- Admission to the Hospital of the University of Pennsylvania Vascular Neurology service
- Incident or recurrent:
 - Ischemic stroke: focal neurological deficit of likely ischemic vascular origin
 - Intracerebral hemorrhage: blood seen on initial head CT

- Transient Ischemic attack: focal neurological deficit of likely ischemic vascular origin that has clinically resolved

4.2 Exclusion Criteria

- Pregnancy
- Comfort or hospice care
- Severe dementia prior to stroke
- Non-communicative and have no family/social support

4.3 Subject Recruitment

Patients will not be formally recruited for this study, but instead enrolled upon admission to the Vascular Neurology inpatient service.

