4.5 Total Number of Patients and Sites

The Hospital of the University of Pennsylvania will be our only enrollment site. We plan to enroll 180 patients in each arm of the trial. At this site, there are approximately 700-800 stroke patients admitted per year, so we anticipate recruitment will require approximately 7 months.

4.6 Vulnerable Populations:

Children, pregnant women, fetuses, neonates, or prisoners are not included in this research study.

5 Study Intervention (Study drug, device, biologic, vaccine, food etc.)

There is no investigational product for this trial as it is a comparative effectiveness study designed to determine whether an attending nurse or standard nursing care improves outcomes for stroke patients. .

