5.5 Subject Compliance Monitoring

Patients will be called at 7, 30, and 90 days following discharge to evaluate their response to the questionnaires. Incomplete response at 7 days will not preclude a phone call directed to patients at 30 and 90 days. Patients who are not reachable via phone interview will not undergo an analysis of their clinical data due to lack of consent.

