7.3 Sample Size and Power Determination

For this pilot project, we anticipate that 65% of patients in the control arm will be adherent to medications (MMAS-4 < 2) based on literature reporting 60%¹⁶ adherence as evaluated using these scales in stroke patients and 70%²¹ adherence in patients with hypertension. To achieve success on the primary endpoint, we estimate that patients must improve to by 15% in order to make this intervention worthy of future investigation in a larger study. Assuming an alpha of 0.05 and a power of 80%, with a 1:1 assignment to each arm, we will require 186 patients in each arm for a total of 372 patients. With that number of patients

we will be able to powered to detect a very small difference of 0.3 (delta = .15 (SD=2)) in the mean scores of the SPER based on the published data.¹⁷ Each outcome will be evaluated independently so that we will not need to make any power readjustments. Readmission rates at 30 days are typically low⁴ and likely lower at our institution based on prior data so we will be underpowered for this outcome. Clinically differences on the SIS will depend on the initial stroke severity of patients within each group and therefore the study cannot be powered for this secondary endpoint.

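### The power figures in 7.3 rest on 186 patients per arm with no allowance for loss, while 4.5 enrols 180 per arm counted before consent, so they do not describe the planned day-7 and day-90 tests

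*Combined protocol and SAP*

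**What the plan says.** Enrolment takes place on admission, under a waiver of consent. Section 4.3: "Patients will not be formally recruited for this study, but instead enrolled upon admission to the Vascular Neurology inpatient service". Section 4.5 sets the target on that basis: "We plan to enroll 180 patients in each arm of the trial".

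Verbal consent is sought at the 7-day call (11.4). The primary outcomes, MMAS-4 adherence and SPER score, are compared at days 7 and 90 (7.1) and come only from telephone interviews (6.3). Section 3.1 expunges the data of patients who decline altogether, and lets others agree to chart review alone, which provides neither primary outcome. On patients who are never reached, 5.5 says: "Patients who are not reachable via phone interview will not undergo an analysis of their clinical data due to lack of consent".

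Section 7.3 gives the sample size for 80% power at alpha 0.05 with equal allocation: "we will require 186 patients in each arm for a total of 372 patients". Its inputs are a control rate ("we anticipate that 65% of patients in the control arm will be adherent to medications") and an improvement of 15%. For the same number of patients it claims power to detect "a very small difference of 0.3 (delta = .15 (SD=2)) in the mean scores of the SPER". It mentions no refusal, non-contact or death, and gives no expected interview rate. Section 7.5 calls for intention to treat on everyone assigned, using the telephone data, without a method for missing outcomes.

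**The concern.** Power depends on the number of patients who enter the test. Here a patient can count towards the enrolment target, be assigned to an arm, and never provide an MMAS-4 or SPER score. That follows from asking for consent after discharge. The plan does not distinguish patients assigned from patients with an outcome, and its two targets differ (180 in 4.5, 186 in 7.3). Even with no loss at all, 180 enrolled cannot supply 186 analysed.

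What is at stake is how a null result is read, above all at day 90, where losses have had longest to accumulate. A reader relying on 7.3 would believe that the trial had 80% power for the adherence difference and could see a 0.3-point SPER difference. Neither statement is tied to the number of patients the tests will contain.

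**Working it through.** **Inputs.** From 7.3: alpha 0.05 (taken as two-sided; the section does not say), power 80%, control adherence 65%, improvement 15% (taken as absolute, so 80%), SPER SD 2 and difference 0.3, 186 per arm. From 4.5: 180 per arm. From 7.4: Pearson chi-square for MMAS-4 and t-test for SPER. Retention is not in the documents; 60% to 90% of 180 is assumed.

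**1. The plan's own figure.** With p1 = 0.65, p2 = 0.80 and mean 0.725, let

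A = √(2 × 0.725 × 0.275) = 0.6315 and B = √(0.65 × 0.35 + 0.80 × 0.20) = 0.6225.

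n per arm = [(1.960 A + 0.842 B) / 0.15]² = 137.9, so 138.

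The stated 186 is not reproduced at 80% power. A continuity correction gives 151. Power of 90% gives 185, and 138 / 0.75 = 184, but 7.3 states neither 90% power nor a 25% allowance.

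**2. MMAS-4 power by number analysed.** Power = Φ[(0.15 √n − 1.960 A) / B].

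| Analysed per arm | Share of 180 | Power, 65% vs 80% |
|---|---|---|
| 186 | not reachable | 90.3% |
| 180 | 100% | 89.3% |
| 162 | 90% | 86.0% |
| 144 | 80% | 81.7% |
| 138 | 77% | 80.0% |
| 126 | 70% | 76.3% |
| 108 | 60% | 69.7% |

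The break-even is 138 / 180 = 76.7%, a loss of about 23%. Starting from 186 enrolled it would be 138 / 186 = 74.2%, a loss of about 26%.

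**3. SPER.** Difference detectable with 80% power = 2 × √(2/n) × (1.960 + 0.842).

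- n = 186: 0.58 points
- n = 162: 0.62 points
- n = 108: 0.76 points

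For a true difference of 0.3, power at 186 is Φ[0.3 / (2√(2/186)) − 1.960] = 0.30. Reaching 80% would take 2 × [2 × (1.960 + 0.842) / 0.3]² ≈ 698 per arm. The 0.3 claim therefore fails with every one of 186 patients analysed.

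**The case against.** The best defence is that 7.3 never calls its 186 the number analysed, and that 186 is well above the 138 its inputs need. The surplus could be an unstated allowance of about a quarter. On that view the adherence comparison keeps 80% power through moderate loss. The arithmetic of this stands: 162 or 144 analysed per arm still give more than 80%. What does not stand is crediting the surplus as a planned allowance, since 7.3 mentions none.

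Several features also limit loss. Proxy answers are accepted (6.3.1), a missed 7-day interview does not rule out later calls (5.5), and 4.2 excludes comfort-care patients and non-communicative patients without support. Day 7 is a primary comparison in its own right and does not depend on a day-90 answer. These points argue for modest loss, but none of them supplies a rate.

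Three stronger readings are tempting, and the documents do not support them:

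- A reader might infer that loss must take MMAS-4 power below 80%. That happens only if fewer than 138 per arm are analysed, and no document says so.
- A reader might blame the SPER shortfall on the consent design. Loss only widens a gap that exists at 186.
- A reader might take the 15% as relative (65% to 74.75%) and cite the low power that results. Power is then about 54% at 186 before any loss, so that is a question about the effect size, not about retention.

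**Conclusion.** The point holds as a mismatch between the number of patients behind 7.3 and the number the design can test. Fewer than 186 per arm will enter either primary comparison, because 4.5 enrols 180 and some of those will decline or not be reached.

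For MMAS-4 the direction of the error depends on retention. On the 65% versus 80% reading, power runs from 86% at 90% retention of 180 to 70% at 60%, and the stated 80% needs at least 77%. For SPER the stated 0.3 is wrong whatever the retention; the detectable difference is 0.58 at 186 and 0.62 to 0.76 over the same assumed range.

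These figures rest on a two-sided 0.05 test, no continuity correction, an SD of 2, and retention rates assumed for want of any in the documents. A reader might also infer that recruitment must stop once the admission count is reached. Section 4.5 describes a plan to enrol and states no such stopping rule.

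**What to change.** In 4.5 and 7.3:

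- Reconcile 180 with 186. Say which number is assigned at admission and which is expected to have a primary outcome.
- State an assumed interview rate at day 7 and at day 90, each with a range and its source. The piloting in 1.2.1 reports only how long the instruments take to administer, so it cannot be cited for a contact or consent rate.
- Restate MMAS-4 power and the detectable SPER difference at those evaluable numbers, separately for the two days. Say whether the 15% is absolute or relative, and replace the 0.3-point claim.

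Reporting completed interviews per arm alongside admissions during the trial would show early whether the evaluable number is on course.

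The cost is some wording and a recalculated table. No extra patients are needed. The SPER figure becomes less favourable; the MMAS-4 figure may rise or fall relative to 80%, depending on the rate assumed.

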4.4 Duration of Study Participation

For each subject, the study intervention phase will vary as this phase will depend on the duration of each individual inpatient admission. The follow up time period will extend to 90 days after discharge for all patients.

4.5 Total Number of Patients and Sites

The Hospital of the University of Pennsylvania will be our only enrollment site. We plan to enroll 180 patients in each arm of the trial. At this site, there are approximately 700-800 stroke patients admitted per year, so we anticipate recruitment will require approximately 7 months.

4.6 Vulnerable Populations:

Children, pregnant women, fetuses, neonates, or prisoners are not included in this research study.

5 Study Intervention (Study drug, device, biologic, vaccine, food etc.)

There is no investigational product for this trial as it is a comparative effectiveness study designed to determine whether an attending nurse or standard nursing care improves outcomes for stroke patients. .

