3.1 General Design

We propose a phase III comparative effectiveness study to evaluate the added value of an attending nurse to the inpatient care of stroke patients compared to routine care. Both types of care are currently available on the inpatient Vascular Neurology service at the Hospital of the University of Pennsylvania as well as at other institutions. Currently, the nurse attending works randomly with patient she selects based on her availability.

In the standard model of inpatient nursing care, stroke education is provided largely in the form of pamphlets distributed to patients and their families. Patients are cared for by a team of physicians and staff nurses with access to social workers and case managers, however, staff nurses do not routinely round on their patients with other members of the care team.

Screening of patients for this trial will occur once the clinical decision to admit a patient to the Vascular Neurology service has been made. All patients who meet inclusion criteria will be assigned to a study arm, addition of an attending nurse versus routine nursing care, according to the day of the week they are admitted to the hospital. Patients who are admitted on even numbered week days will have their care supplemented by the attending nurse. This is effectively a stratified random assignment, as there are no clinical or systematic features that otherwise are associated with odd or even numbered days. The duration of the intervention will depend on the duration of a patient's hospital admission.

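### The protocol states two sample sizes (360 and 372), and its 7-month recruitment forecast leaves weekend admissions unsettled and allows for no exclusion, refusal or non-contact

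*Combined protocol and SAP*

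**What the plan says.** Section 4.5 gives the planned size as "We plan to enroll 180 patients in each arm of the trial", that is 360, and the timeline as "there are approximately 700-800 stroke patients admitted per year, so we anticipate recruitment will require approximately 7 months". Section 7.3 gives a different size: "we will require 186 patients in each arm for a total of 372 patients". The Study Summary also gives 372.

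The inputs to that size are in 7.3: "Assuming an alpha of 0.05 and a power of 80%, with a 1:1 assignment to each arm", "we anticipate that 65% of patients in the control arm will be adherent to medications", and an effect worded as "we estimate that patients must improve to by 15" percent.

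On who is assigned, the text points two ways. Section 3.1.3 defines both arms by weekday of admission; for the control arm, "patients admitted on odd-numbered weekdays will get usual routine care". The caseload rule in 5.2 is also written for weekdays. Yet 3.1 says that "All patients who meet inclusion criteria will be assigned to a study arm", another sentence of 3.1.3 speaks of even-numbered days without a weekday limit, 6.2 refers only to the admission date, and the eligibility criteria in 4.1 and 4.2 do not exclude weekend admissions.

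The Study Summary lists 7 months as the study duration, while 4.4 follows every patient for 90 days after discharge. Section 10.1 describes 6 months of data collection, then a month of cleaning and a month of analysis.

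**The concern.** The forecast goes from annual admissions straight to a duration. The protocol itself guarantees losses in between: the exclusions in 4.2, consent sought only at the 7-day call (11.4), no analysis of clinical data for patients who cannot be reached (5.5), and removal of data for those who fully decline (3.1). No rate is given for any of these. If weekend admissions have no arm, the pool shrinks further.

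Three things are at stake: which patients are in the trial, how long enrolment must run, and how many analysable patients the team should expect. The two stated sizes also leave no single number at which enrolment is complete.

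**Working it through.** **Inputs from the documents.** 700-800 admissions a year and 7 months (4.5); 360 (4.5) or 372 (7.3, Study Summary); control adherence 65%, improvement 15%, alpha 0.05, power 80%, 1:1 (7.3).

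**Assumptions.** Five-sevenths of admissions fall on weekdays; the documents give no share. The 15% is an absolute difference (65% versus 80%). Alpha is two-sided; 7.3 does not say. The arms are equal in size.

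**1. The plan's own 7 months.** Months = N / (annual admissions / 12), all days, 100% yield:
- 360: 360/(800/12) = 5.4 to 360/(700/12) = 6.2 months
- 372: 372/(800/12) = 5.6 to 372/(700/12) = 6.4 months

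Seven months is therefore not reproduced at full yield. It implies an unstated yield, calculated in step 2.

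**2. All days count.** Supply in 7 months: 700 × 7/12 = 408; 800 × 7/12 = 467. Yield needed:
- 372: 372/467 = 80% to 372/408 = 91%
- 360: 360/467 = 77% to 360/408 = 88%

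For 372, that leaves room for a total loss of 9-20%.

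**3. Weekdays only.** Supply in 7 months: 408.3 × 5/7 = 292; 466.7 × 5/7 = 333. Shortfall at 100% yield:
- against 372: 372 − 333 = 39 to 372 − 292 = 80
- against 360: 360 − 333 = 27 to 360 − 292 = 68

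Months needed at 100% yield:
- 372: 372/(800 × 5/84) = 7.8 to 372/(700 × 5/84) = 8.9
- 360: 7.6 to 8.6

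Sensitivity to the 5/7: with no other loss, 372 is reached in 7 months only if 80-91% of admissions fall on weekdays (the same ratios as in step 2), against 71% if admissions are even.

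**4. The stated size and power.** With p1 = 0.65, p2 = 0.80 and pooled p = 0.725,

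n per arm = [z(0.975)·√(2·0.725·0.275) + z(power)·√(0.65·0.35 + 0.80·0.20)]² / 0.15²

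- 80% power: 138 per arm, 276 in total (151 and 302 with continuity correction)
- 90% power: 185 per arm, 370 in total

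The 186 of 7.3 is not reproduced at 80% power; 186 per arm gives 90.3%, and the 180 of 4.5 gives 89.3%. Inflating for dropout could lead from 138 to about 186 (about 25-26% loss), but 7.3 states no dropout rate.

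**5. Power at what 7 months might supply, weekdays only.**

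| Yield | Total | Per arm | Power |
|---|---|---|---|
| 100% | 292-333 | 146-166 | 82-87% |
| 70-80% (assumed) | 204-267 | 102-133 | 67-79% |

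The second row is 292 × 0.70 = 204 and 333 × 0.80 = 267. To keep 80% power, 276 patients would have to come from the weekday supply, a yield of 276/333 = 83% to 276/292 = 95%. At the assumed 70-80% yield, 372 would take 372/(800 × 5/84 × 0.80) = 9.8 to 372/(700 × 5/84 × 0.70) = 12.8 months.

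**6. Duration.** Recruitment of 7 months (4.5) plus 90 days of follow-up exceeds the 7-month study duration in the Study Summary. If 7 months is the whole study, enrolment lasts about 7 − 3 = 4 months, which supplies 233-267 admissions with all days counted, below both targets.

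**The case against.** A reader might infer that the trial cannot reach its size in 7 months. The documents do not support that. It requires weekend admissions to be unassigned, and no passage says they are; 3.1, 6.2 and part of 3.1.3 point the other way. With all days counted, gross supply exceeds both targets. The 5/7 factor is also an assumption, not a figure from the protocol.

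A reader might also infer that falling short of 372 makes the trial underpowered. That does not follow. The stated power is 80%, which on the stated inputs needs about 276 patients, and even the full weekday supply exceeds that. The fall below 80% rests on a 70-80% yield for which the documents give no basis. At the top of that range power is 78.5%, close to plan; only the lower end is clearly short.

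Finally, 4.5 words its 7 months as an approximate expectation, and no rule closes enrolment at that date. If enrolment runs to target, the weekday reading at full yield costs about one to two months.

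All of this stands, and it limits the point. It does not remove the two conflicting sizes, the undefined handling of weekend admissions, the absence of any allowance for losses, or the clash between the study duration and the 90-day follow-up.

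**Conclusion.** The point holds in conditional form. The conflict between 360 and 372 needs no assumption; it is 12 patients, about 3%, and has almost no effect on power. The recruitment forecast is unsupported on either reading. The weekday reading falls short of both targets before any other loss, given even admissions over the week. The all-days reading works only at a high yield that the plan neither states nor justifies. Loss of the stated 80% power is possible, not demonstrated: it depends on the weekday reading, on enrolment stopping at 7 months, and on an assumed yield below 83-95%. The correction should be made, because the number of patients and who is enrolled are basic to the trial, but this is not a flaw in the analysis method.

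**What to change.** 1. Reconcile 4.5 with 7.3 and the Study Summary, and state one size with the power it gives. Simply adopting 186 per arm would leave an error in place: it corresponds to about 90% power for 65% versus 80%, not 80%. If 186 was meant to include an allowance for loss, state the rate.
2. State in 3.1.3 and 4.5 whether weekend admissions are assigned and, if so, how; align 3.1, 5.2 and 6.2.
3. Restate the recruitment period as eligible admissions per month times an explicit fraction who are eligible, reached and consenting. Show it separately from the 90-day follow-up, and bring the study duration in the Study Summary and the periods in 10.1 into line.
4. Close enrolment on the number of consented patients, not on a date.

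These are changes of protocol wording. The cost is a longer stated timeline, or a smaller stated size with its lower power given openly.
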